10.8.1 Ceramides

In this study, ceramides will be analyzed by, and according to a method developed by Dr. [REDACTED] [REDACTED]). Details of collection, storage and processing are provided in the Study Reference Manual and when instructed to do so, prepare all the samples in need of shipment to the designated central lab [REDACTED], for dispatch to the specialist laboratory [REDACTED], Czech Republic.

10.8.2 Metabolipidomics

In this study, the metabolipidomic analysis will consist in quantifying eicosanoid metabolites (specific AA-derived leukotrienes, lipoxins, prostaglandins and thromboxane) and docosanoid metabolites (specific DHA-derived resolvins, protectins and maresins) in plasma phospholipids. Metabolite levels will be analyzed quantitatively by assessing the molecular decomposition using a LC/MS/MS method.

Details of collection, storage and processing are provided in the Study Reference Manual and when instructed to do so, prepare all the samples in need of shipment to the designated central lab [REDACTED], for dispatch to the specialist laboratory [REDACTED], The Netherlands.

10.8.3 Systemic bone formation/resorption markers

The selected markers are serum osteocalcin, serum C-telopeptide (CTx) and serum P1NP. Samples will be obtained at the time points listed in the Schedule of Events, page 10, specifically on Days 1 and 161 (Visits #2 and 7, respectively). Details of collection and processing are provided in the Study Reference Manual and when instructed to do so in the Study Reference Manual, prepare all the samples in need of shipment to the designated central laboratory [REDACTED], Tennessee [REDACTED], USA.

10.8.4 Markers of oxidative stress

Blood samples for the scheduled determination of systemic markers of oxidative stress will be obtained at the time points listed in the Schedule of Events, page 10, specifically on Days 1, 21 and 161 (Visits #2, 3 and 7, respectively).

Details of collection, storage and processing are provided in the Study Reference Manual and when instructed to do so, prepare all the samples in need of shipment to the designated central lab [REDACTED], for dispatch to the specialist laboratory, [REDACTED], Aurora, CO.

10.9 Bone density

The bone density will be determined at time points listed in the Schedule of Events, Page 10, specifically on Days 1 and 189 (Visits #2 and 8, respectively), at selected sites and in the first 24 patients who volunteer to participate in this additional investigation at the given study sites. The lumbar spine bone mineral density will be measured with a dual X-ray absorptiometry (DXA) instrument. Specifics to ensure consistency of DXA measurement such as the expression of results as a Z-score normalized according to age and gender, the need to use the same instrument and the need to follow the institutional procedure to ensure within-patient comparability of measurements will be described in the Study Reference Manual.

10.10 Matouk Disease Score

The Matouk disease score will be determined at time points listed in the Schedule of Events, Page 10, specifically on Days 1, 77, 161, 189, (Visits #2, 5, 7 and 8, respectively), at selected sites who will volunteer to participate in this exploratory investigation. The objective of this investigation is to further validate the Score in the framework of a well controlled therapeutic study. An example of the subsection questionnaires is presented in the Study Reference Manual. Given the lack of recognized biomarkers for CF inflammation clinical studies, and the long time required for FEV₁ to show changes, we believe that exploring additional alternatives will be welcomed by the CF community.

The Matouk Disease Score was previously published^{97, 98}, and reviewed by Hafen⁹⁹ and was used recently in two studies; 1- A non-interventional study on pulmonary exacerbations by [name] and 2- A Phase Ib study of fenretinide^{3, 100}. Hafen recommends Matouk scoring as a potential tool to assess the clinical response to various treatment regimens on a short-term basis. The validation showed its value in prognostic evaluation of patients in end-stage disease, providing better discrimination for survival in the last 2 years of life than FEV₁ % predicted alone⁹⁸.

The Matouk Disease Score is a sum comprised of four subsections: clinical, pulmonary function tests (PFT), chest radiographic score (CXR) and complications score. The 3 key subsections with high impact on the total score internal consistency are the Clinical, the PFT and the Complication subsections. The CXR score is not essential for the Matouk score to perform well. If a new CXR is available, then its grading is used. Otherwise, the most recent CXR can be used instead. In the absence of a CXR, the radiographic score is omitted, and the total score internal consistency, as depicted by the Cronbach's coefficient alpha, is preserved. Consequently, the CXR score is optional.

The clinical subsection involves the evaluation of the patient's symptoms by the physician. The symptoms evaluated are weight, weight change, dyspnea, cough frequency, sputum colour, thickness and volume, physical examination (air entry, crackles, hyperinflation), respiratory rate/cardiac frequency, sputum culture, appetite and general condition.

The PFT subscore is based on the results of pulmonary function test.

The complication sub-score tabulates the serious events that are known to negatively impact CF disease: pulmonary exacerbation requiring therapy, pneumothorax, haemoptysis, respiratory failure, cardiac enlargement or congestive heart failure and pulmonary surgery.

The CXR score is the evaluation of the chest x-ray [optional in this study]

For the clinical subsection, the PFT and CXR subscores, the higher the better. For the complications score, the lower score is better. The total score is calculated by subtracting the complications score from the three subscores (total score = clinical + PFT + CXR (if available) – Complications).

The score uses information and measurements that should already be available at the clinical site. To facilitate the data entry/capture, the Sponsor will develop clear and simple templates to collect such data, and training will be provided. The sites will be instructed to send the completed forms to a centralized location for scoring and interpretation.

11 SAFETY ASSESSMENTS

Safety evaluations will include reporting of Adverse Events (AEs), clinical laboratory assessments, clinical evaluation of vital signs, ECGs, as well as ophthalmological questionnaires and examinations.

11.1 Adverse Events

All AEs will be assessed, documented, and reported in accordance with ICH GCP guidelines.

11.1.1 Documentation of Adverse Events

Adverse events will be collected from the time of informed consent until the last scheduled study follow-up, 4 weeks after the last dose of the study drug, or until the last unscheduled safety-related assessment whichever occurs latest. An AE is any untoward medical occurrence (which does not necessarily have to have a causal relationship with this treatment). An AE can be any unfavorable and unintended sign (including an abnormal laboratory finding, for example), symptom, or disease temporally associated with the use of an investigational product, whether or not related to the study drug. This includes any occurrence that was new in onset or aggravated in severity or frequency from the baseline condition. Planned hospital admissions or surgical procedures for an illness or disease that existed before the patient was screened in the study are **not** to be considered AEs unless the condition deteriorated in an unexpected manner during the study (e.g. surgery was performed earlier than planned).

Abnormal results of diagnostic procedures, including laboratory test abnormalities, are considered AEs if they result in any one of the following:

- Discontinuation of study treatment;
- Require treatment or any other therapeutic intervention;
- The necessity for further diagnostic evaluation (excluding a repetition of the same procedure to confirm the abnormality);
- Association with clinical signs or symptoms that may have a significant clinical impact, as determined by the Investigator.

Patients are encouraged to report AEs spontaneously or in response to general, non-directed questioning. All AEs are to be followed until resolution or until a stable clinical endpoint is reached. The investigator should question patients about AEs and changes in pre-existing illnesses since their last visit and must record the information in the patients' medical records. The onset and end dates, severity, relationship to study agent, action taken, and outcome must be recorded for each AE. All AEs are to be recorded on the appropriate e-CRF and in detail on the source documents.

Any AE that occurs within 4 weeks following the last dose of the study drug will be considered treatment emergent (TEAe) and must be recorded in the e-CRF and, if an SAE, reported immediately to the Sponsor. Adverse events that are ongoing at the end of the 4-week follow-up period should be marked as ongoing. However, it is the responsibility of the Investigator to follow up on these events until resolution, according to standard medical care.

Any AE or SAE that the investigator becomes aware of outside of the reporting period until the end of the study that has or is believed to have a causal relationship to the study drug should be reported to Laurent

Pharmaceuticals via telephone. Patients who experience AEs will be monitored with relevant clinical assessments and laboratory tests, as determined by the Investigator. All AEs and laboratory abnormalities encountered during the study should be followed until resolution or stabilization of the event(s). Any action taken and follow-up results must be recorded in the patient's medical record. Follow-up laboratory results should be filed with the patient's source documentation and e-CRF. For all AEs that require the patient to discontinue treatment, relevant clinical assessments and laboratory tests should be repeated on at least a monthly basis until final resolution or stabilization of the event(s). These assessments should be captured in the source data and SAE forms but will not be entered in the e-CRF.

All AEs for randomized patients will be recorded in the e-CRF and the patient's source documents. AEs for patients who are screened but not subsequently randomized in the study will be recorded only in the patient's source documents. The following data should be documented for each AE:

- Description of the event;
- Classification of "serious" or "not serious";
- Date of first occurrence and date of resolution (if applicable);
- Severity;
- Causal relationship to study drug(s);
- Action taken;
- Outcome;
- Concomitant medication or other treatment given

An independent DSMB will assess AEs that are reported from study sites. The DSMB will meet at regular intervals throughout the duration of the study or will meet as determined by the DSMB chair, and may recommend systematic treatment arm dose reduction or early termination of the study for safety reasons (see Sections 7.2.4 and 7.2.2).

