ⁱⁱⁱ Specific Dark adaptation tests: May consist either of a dark adaptometry test performed with a dark adaptometer or equivalent **OR** a full field ERG test of the scotopic vision, and if possible the photopic vision, after dark adapting and light-adapting the patient, respectively. The order of testing may be done according to specific equipment in use.

vitreous humor, fundus examination of retina and retinal vessels, fundus visualization of optic nerve and macula.

The ad-hoc ophthalmologic examinations may differ since directed to potential medical condition based on the referral by the study Investigator. Such on-demand examinations should be recorded in detail, with results appended, in the proper unscheduled event e-CRF. The Medical Monitor should be notified of any additional ophthalmologic examinations.

The results of the post-study scheduled examination and any ad-hoc examination must be contrasted with the baseline ophthalmologic examination and any new adverse finding should be reported as an AE. Those that meet the definition of clinically significant assessment (see section 11.1.2 on clinically significant assessments) should be brought to the attention of the Medical Monitor, for forwarding to the DSMB.

The use of an ERG in lieu of the dark adaptometry test waives the need for further second line ERG testing, unless requested by the ophthalmologist. In extenuating circumstances such as the inability to locate the equipment to perform the above specific dark adaptation testing despite thorough feasibility assessments, such testing may be waived for a given clinical site. In all cases however, the site must have access, even distally, to an ERG in case a second line ERG examination is requested.

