12.5.2 Clinical Laboratory Assessments

Safety laboratory variables (e.g., hematology, biochemistry, and urinalysis results) will be presented in SI units at each time point using descriptive statistics (mean, standard deviation, median, minimum, and maximum). Change from baseline values for each variable will also be presented by treatment group. The number and percentage of patients with shift changes from baseline (normal/missing, high, and low according to the reference range) to the highest/lowest laboratory evaluation during the TEAE period will be tabulated by treatment group.

Summary tables of laboratory results will be prepared to examine the worst toxicity grade on study. Cross-tabulations of patients by maximum post-baseline toxicity will be presented, as appropriate. Patients who develop Grade 3-4 laboratory toxicities will also be listed separately.

A Fisher's Exact test will be used in an exploratory sense to evaluate differences between treatment groups in the incidence of laboratory toxicities graded according to CTCAE grading outlined in section 11.1.1.1.

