13 DATA HANDLING AND RECORD KEEPING

13.1 Case Report Forms

All patient data generated by the study will be recorded in each patient's e-CRFs. Data reported on the e-CRFs that are derived from source documents should be consistent with the source documents or the discrepancies should be explained. e-CRFs will be considered complete when all missing and/or incorrect data have been resolved and all safety data have been recorded.

The Investigator, or designated representative, should complete the e-CRF as soon as possible after information is collected. e-CRFs must be completed only by persons designated by the Investigator. The e-CRF system should enable an audit trail that will provide the user's identification information and the date and time of any entry/correction. The completed e-CRF will be reviewed by Laurent Pharmaceuticals or its agents on a routine basis.

The Investigator must approve formally all the information in the e-CRFs for the patients for whom he/she is responsible. The United States Food and Drug Administration (FDA) may inspect all records related to the study.

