3.9 Clinical Laboratory Assessments

Safety laboratory variables (i.e. hematology, biochemistry, and urinalysis results) will be presented in SI units at each time point using descriptive statistics (mean, standard deviation, median, minimum, and maximum). Change from baseline values for each variable will also be presented by treatment group. The number and percentage of patients with shift changes from baseline (normal/missing, high, and low according to the reference range) to the highest/lowest laboratory evaluation during the TEAE period will be tabulated by treatment group.

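### Protocol 11.1.1 contradicts itself on whether follow-up of treatment-stopping adverse events enters the e-CRF, so some unscheduled values could be missing from the worst-value and ad-hoc eye summaries

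*Protocol*

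**What the plan says.** Protocol 11.1.1 (Documentation of Adverse Events) gives two rules within a few sentences. The general rule is "Follow-up laboratory results should be filed with the patient's source documentation and e-CRF". The text then turns to AEs that require the patient to discontinue treatment, asks for relevant clinical assessments and laboratory tests at least monthly until resolution or stabilization, and ends: "These assessments should be captured in the source data and SAE forms but will not be entered in the e-CRF".

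Other sections point to the e-CRF:
- Protocol 13.1: "All patient data generated by the study will be recorded in each patient's e-CRFs".
- Protocol 11.5, on ad-hoc eye examinations: "Such on-demand examinations should be recorded in detail, with results appended, in the proper unscheduled event e-CRF".
- Protocol 11.4 sends additional ECGs to the unscheduled-event e-CRF. It also asks for close QTc monitoring after treatment is stopped for a prolonged QTc.

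Three planned outputs draw on such values:
- Both Protocol 12.5.2 and SAP 3.9 plan a laboratory shift table from baseline "to the highest/lowest laboratory evaluation during the TEAE period will be tabulated by treatment group".
- Protocol 12.5.2 adds: "Summary tables of laboratory results will be prepared to examine the worst toxicity grade on study".
- Protocol 12.5.5 and SAP 3.10 present ad-hoc eye examinations against baseline and tabulate objectively confirmed symptoms separately.

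**The concern.** A site cannot obey both sentences of 11.1.1 for the same patient. For someone who stops because of a raised liver test, one sentence sends the repeat test to the e-CRF and the other keeps it out. With 35-40 planned centers, practice may differ between sites.

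The named alternative store is also incomplete. A non-serious AE can lead to discontinuation without generating an SAE form, so its follow-up results could stay in source documents only.

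The patients concerned are, by definition, those with treatment-stopping toxicity, and safety and tolerability is one of the two primary endpoints. A peak or recovery value seen only at an unscheduled assessment could therefore be absent from summaries meant to show the worst value.

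**Working it through.** The plan states no figure to reproduce. The check has two parts: which data the bar reaches, and when scheduled visits would cover the gap.

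**1. Which data the bar reaches**

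| Data after stopping for an AE | Rule | Barred from e-CRF? |
|---|---|---|
| AE record: dates, severity, action taken, outcome | 11.1.1: every AE goes in the e-CRF | No |
| Planned visits, or at minimum a visit 4 weeks after the last dose | 8.4 and introduction to 12 | No |
| Unscheduled repeat laboratory tests | 11.1.1, two rules | Contradictory |
| Other unscheduled clinical assessments | 11.1.1 against 13.1 | Contradictory |
| Additional ECGs, on-demand eye examinations | 11.4 and 11.5 against 11.1.1 | Contradictory; the specific rules say enter them |

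Only the last three rows are at risk.

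**2. Does a scheduled laboratory visit fall within 28 days of the last dose?**

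Inputs:
- Post-baseline laboratory visits on Days 21, 49, 77, 105, 161 and 189 (Protocol section 2).
- Six cycles of 21 days on and 7 off (9.5), giving 6 × 21 = 126 possible last-dose days.
- A treatment-emergent (TEAE) window of 4 weeks = 28 days after the last dose (11.1.1).

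For a last dose on day s, look for a visit on day v with s < v ≤ s + 28, using nominal days.

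| Cycle (dosing days) | Next scheduled laboratory visit | Covered | Not covered |
|---|---|---|---|
| 1 (1-21) | 1-20 → 21; 21 → 49 (28 days) | 21 | 0 |
| 2 (29-49) | 29-48 → 49; 49 → 77 (28 days) | 21 | 0 |
| 3 (57-77) | 57-76 → 77; 77 → 105 (28 days) | 21 | 0 |
| 4 (85-105) | 85-104 → 105; 105 → 161 (56 days) | 20 | 1 |
| 5 (113-133) | 113-132 → 161 (48 to 29 days); 133 → 161 (28 days) | 1 | 20 |
| 6 (141-161) | 141-160 → 161; 161 → 189 (28 days) | 21 | 0 |
| Total | | 105 | 21 |

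For the 21 uncovered days (Day 105 and Days 113-132), a patient on the planned-visit route has only unscheduled values inside the 28-day window. A patient on the minimum route has the 4-week visit.

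**3. Timing of the repeats**

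With exactly monthly repeats, the first falls at about the edge of the window and later ones fall outside it. Values well inside the window arise only if repeats are more frequent, which the at-least-monthly wording allows.

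**4. Eye examinations, same count**

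After screening, complete examinations are scheduled on Days 77 and 189. One follows within 28 days for last doses on Day 49, Days 57-76 and Day 161: 1 + 20 + 1 = 22 of 126, leaving 104. This matters only if the general bar in 11.1.1 is read as overriding the specific rule in 11.5.

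**The case against.** The strongest reply is that little is actually lost, and much of it stands.

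- **Scheduled data remain.** Patients who stop for toxicity stay on planned visits or attend a 4-week visit, and nothing bars those data. A reader might infer that the safety tables lose all post-stop values. The documents do not support that.
- **AE tables remain.** A laboratory abnormality that stops treatment is itself an AE. Protocol 12.5.1 and SAP 3.18 tabulate TEAEs by maximal severity, and Protocol 12.5.1 lists Grade 3-4 toxicities. A severe peak should still show there.
- **The shift table is coarse.** It uses reference-range categories. A patient stopped for a high value is normally already counted as high, so missing a later, higher peak would not move that category. The worst-grade table is more sensitive, but SAP 3.9 does not repeat it.
- **Eye data have their own rule.** Protocol 11.5 sends on-demand examinations to the e-CRF and SAP 3.10 presents them. A reader might infer that reversibility of nyctalopia would rest on the AE outcome field alone. That requires 11.1.1 to override 11.5, which no text says.
- **Central laboratory.** Protocol 11.2 makes central results primary. If they reach the database by direct transfer, the laboratory loss shrinks. The documents do not describe a transfer, and it would not cover clinical or eye assessments or local urgent tests.

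None of this removes the contradiction or supplies a store for follow-up values of non-serious AEs.

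**Conclusion.** The contradiction is real and the text is wrong as written. The consequence is limited: some unscheduled post-discontinuation values could be missing from the highest/lowest shift table, the protocol's worst-grade table and, if 11.1.1 is taken to override 11.5, the ad-hoc eye summaries. For laboratory values, exposure is clearest for 21 of 126 possible last-dose days on the planned-visit route. That counts calendar days, not patients, so it does not estimate how many patients would be affected.

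The count assumes nominal visit days and a TEAE window of exactly 28 days. Protocol 12.5.1 ends the period at the last follow-up, planned for 4 weeks after the last dose. If that means the actual last visit, later scheduled values count too and the exposure is smaller.

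A reader might also infer that toxicity on LAU-7b would be understated. That needs more toxicity-related stops on LAU-7b than on placebo, and informative values seen only at unscheduled visits. The documents give no figure for either, so the size and direction of any arm difference are unknown. SAP section 5 makes the AE comparison descriptive, without Fisher's exact test, so no planned safety test changes.

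**What to change.** In Protocol 11.1.1, replace the last sentence on follow-up of treatment-stopping AEs. Require that unscheduled assessments following an AE that led to treatment discontinuation be entered in the existing unscheduled-event e-CRF, at least through the TEAE period and the last on-study visit. They should also be kept in source, and on SAE forms where the event is serious. This brings the section into line with 11.4, 11.5 and 13.1.

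In SAP 3.9, state that these values count in the highest/lowest and worst-grade summaries. SAP 3.10 already presents ad-hoc eye examinations and needs no more than a cross-reference.

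The cost is protocol and SAP wording plus a small amount of data entry. The assessments are already ordered and the e-CRF pages already exist.
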